2. TRIAL OBJECTIVES

The protocol defined the trial objectives as:

2.1 Primary Objective

Blinded Phase:

To evaluate the efficacy of GWP42003-P as add-on therapy in reducing the frequency of seizures when compared with placebo in patients with TSC.

Open-label Extension:

To evaluate via the adverse events (AE) profile the long term safety and tolerability of GWP42003-P as add-on therapy in children and adults with TSC who experience inadequately-controlled seizures.

2.2 Secondary Objectives

Blinded Phase:

- To evaluate the effect of GWP42003-P compared with placebo on antiepileptic measures.
- To evaluate the effect of GWP42003-P on growth and development (in patients less than 18 years old) compared with placebo.
- To evaluate the effects of GWP42003-P on quality of life compared with placebo.
- To evaluate the safety and tolerability of GWP42003-P compared with placebo.

Open-label Extension:

- To evaluate the long term effects of GWP42003-P, as add-on therapy, on antiepileptic measures.
- To evaluate the long term effect of GWP42003-P on growth and development (in patients less than 18 years old).
- To evaluate the long term effects of GWP42003-P on quality of life.
- To evaluate the long term safety and tolerability of GWP42003-P.

2.3 Exploratory Objectives

Blinded Phase:

- To evaluate the effect of GWP42003-P on TSC-associated neuropsychiatric disorders (TAND), including cognitive and behavioral function and autistic features compared with placebo.
- To determine the pharmacokinetics (PK) of CBD, and its major metabolites following single and multiple doses of GWP42003-P.
- To evaluate the effects of GWP42003-P on plasma concentrations of concomitant AEDs, if applicable.

Open-label Extension:

- To evaluate the long term effect of GWP42003-P on TAND, including cognitive and behavioral function and autistic features compared with placebo.

3. INVESTIGATIONAL PLAN

3.1 Trial Design

This multicenter trial consists of a randomized, placebo-controlled, double-blind phase followed by an open-label extension (OLE) phase.

Blinded Phase:

The blinded phase of the trial is a randomized, double-blind, parallel-group, 16-week comparison of two doses of GWP42003-P vs. placebo. Patients will complete a 1-week screening period and a 4-week baseline period before they are randomized to receive either 25 mg/kg/day GWP42003-P, 50 mg/kg/day GWP42003 P or placebo. Randomization will be stratified by age according to the following ranges: 1–6, 7–11, 12–17 years and 18–65 years. Patients will begin a 4-week dose escalation period, titrating up to their assigned dose, before continuing on a stable dose of blinded Investigational Medicinal Product (IMP) for 12 weeks.

Dose escalation for each patient is subject to the investigator's assessment of safety and tolerability. If a dose becomes poorly tolerated, the investigator may consider temporarily or permanently reducing the dose for the remainder of the trial.

Following completion of the blinded phase, patients will be invited to continue to receive GWP42003-P in an OLE.

Those patients opting not to enter the OLE will complete a 10-day taper period (down-titrating 10% per day for 10 days).

Open-label Extension Transition:

In order to maintain consistent exposure to IMP and maintain the integrity of the blind, patients will enter a 2-week blinded transition to the OLE. OLE IMP will be titrated up to 25 mg/kg/day whilst blinded IMP is simultaneously tapered down to zero. All patients will complete the transition and enter the OLE taking 25 mg/kg/day GWP42003-P:

- Patients from the placebo arm will titrate up to 25 mg/kg/day GWP42003-P.
- Patients from the 25 mg/kg/day GWP42003-P arm will continue to take 25 mg/kg/day GWP42003-P.
- Patients from the 50 mg/kg/day GWP42003-P arm will taper down (10% per day) to 25 mg/kg/day GWP42003-P.

Open-label Extension:

The OLE consists of a 3-week titration period followed by a maintenance period and a 10-day taper period. The initial OLE period will last for a maximum of 1 year.

Following titration according to the titration schedule, patients will continue with their optimal GWP42003-P dose. However, investigators may decrease the dose if a patient experiences intolerance, or increase the dose to a maximum of 50 mg/kg/day if required for better seizure control, until the optimal dose is found.

3.2 Definition of Sample Size

Blinded Phase:

A total of 210 patients will be enrolled. The 210 patients will be randomly allocated to 1 of 4 treatment arms (GWP42003-P 25 mg/kg/day, GWP42003 P 50 mg/kg/day, placebo 25 mg/kg/day dose volume equivalent, or placebo 50 mg/kg/day dose volume equivalent) at a 2:2:1:1 ratio. The placebo arms will be pooled for the analyses of efficacy.

If it is assumed that patients in the placebo arm will experience a mean reduction in seizure frequency of 15% (from baseline), patients receiving GWP42003-P will experience at least a 50% reduction in seizures and a common standard deviation of 60%, then this sample size of 70 patients per arm will be sufficient to detect a difference in response distributions with 90% power. This test is based on a two-sided non-parametric Mann-Whitney-Wilcoxon test for continuous response data with a 5% significance level.

Open-label Extension:

All patients who wish to continue on IMP following the blinded phase.

3.3 Efficacy and Safety Endpoints

3.3.1 Primary Efficacy Endpoint

Blinded Phase:

The primary endpoint is the change in number of TSC associated seizures* during the treatment period (maintenance and titration) compared to baseline in patients taking GWP42003-P compared with placebo.

*Primary endpoint TSC-associated seizures include: focal motor seizures without impairment of consciousness or awareness; focal seizures with impairment of consciousness or awareness; focal seizures evolving to bilateral generalized convulsive seizures and generalized seizures (tonic-clonic, tonic, clonic or atonic) that are countable.

Open-label Extension:

The safety of GWP42003-P will be evaluated by assessing the incidence, type and severity of AEs.

3.3.2 Secondary Efficacy Endpoints

Blinded Phase:

The following endpoints will be compared between treatment arms over the 16-week, double-blind treatment period (all changes relative to baseline):

Key:

1. Number of patients considered treatment responders defined as those with a $\geq 50\%$ reduction in TSC-associated seizure frequency (see Section 5.1.3.7).
2. Change in Caregiver Global Impression of Change (CGIC) or Subject Global Impression of Change (SGIC) score.
3. Change in total seizures.

Other:

Antiepileptic Efficacy Measures:

- Number of patients considered treatment responders defined as those with a $\geq 25\%$, $\geq 50\%$, $\geq 75\%$ or 100% reduction in TSC-associated seizure frequency.
- Number of patients experiencing a $> 25\%$ worsening, $- 25$ to $+ 25\%$ no change, 25–50% improvement, 50–75% improvement or $> 75\%$ improvement in TSC-associated seizure frequency.
- Change in number of TSC-associated seizure-free days.
- Change in number of ‘other’ seizures (absence, myoclonic, focal sensory and infantile/epileptic spasms).

Growth and Development (in patients less than 18 years old):

- Change in serum insulin-like growth factor-1 (IGF-1) levels.
- Change in Tanner Staging score (for patients aged 10–17 [inclusive]).

Quality of Life:

- Changes in the Quality of Life in Childhood Epilepsy (QOLCE; patients 2–18 years) or Quality of Life in Epilepsy (QOLIE-31-P; patients 19+ years) score.
- Change in Physician Global Impression of Change (PGIC) score.

Safety and Tolerability:

- AEs.
- Clinical laboratory parameters.
- 12-lead electrocardiogram (ECG).
- Physical examination parameters.
- Vital signs.
- Columbia-Suicide Severity Rating Scale (C-SSRS: 19+ years) or C-SSRS Children’s (6–18 years) score, where applicable.
- Number of inpatient hospitalizations due to epilepsy.
- Abuse liability.
- Effects on menstruation cycles (in females).

Open Label Extension:

The following endpoints will be assessed relative to the pre-randomization baseline of the blinded phase:

Key:

- Percentage change in number of TSC-associated seizures (average per 28 days).
- Number of patients considered treatment responders defined as those with a $\geq 50\%$ reduction in TSC-associated seizure frequency.
- Change in CGIC or SGIC score.
- Change in total seizures.

Other:

Antiepileptic Efficacy Measures:

- Number of patients considered treatment responders defined as those with a ≥ 25%, ≥ 50%, ≥ 75% or 100% reduction in TSC-associated seizure frequency.
- Number of patients experiencing a > 25% worsening, - 25 to + 25% no change, 25–50% improvement, 50–75% improvement or > 75% improvement in TSC-associated seizure frequency.
- Change in number of TSC-associated seizure-free days.
- Change in number of 'other' seizures (absence, myoclonic, focal sensory and infantile/epileptic spasms).

Growth and Development (patients less than 18 years):

- Change in serum IGF-1 levels.
- Change in Tanner Staging score (for patients aged 10–17 [inclusive]).

Quality of Life:

- Changes in the QOLCE (patients 2–18 years) or QOLIE-31-P (patients 19+ years) score.
- Change in PGIC score.

Safety and Tolerability:

- Clinical laboratory parameters.
- ECG.
- Physical examination parameters (including height and weight).
- Vital signs.
- C-SSRS (19+ years) or C-SSRS Children's (6–18 years) score, where applicable.
- Number of inpatient hospitalizations due to epilepsy.
- Abuse liability.
- Effects on menstruation cycles (in females).

3.3.3 Exploratory Endpoints (Double-blind and Open-label Extension)

Antiepileptic Efficacy Measures:

- Change in composite focal seizure score (frequency × severity).
- Change in number of seizures by subtype.
- Change in use of rescue medication.
- Change in the number of episodes of status epilepticus (convulsive and non-convulsive).
- Changes in duration of seizure subtypes as assessed by the Subject Global Impression of Change in Seizure Duration (SGIC-SD) or the Caregiver Global Impression of Change in Seizure Duration (CGIC-SD).

TAND:

Cognitive and Behavioral Function:

- Changes in Vineland Adaptive Behavior Scales, Second Edition (Vineland-II).

- Changes in Wechsler Scales (pre-school, primary, children, adult).
- Changes in Achenbach Child Behavior Checklists (CBCL) and Adult Behavior Checklist (ABCL).

Autistic Features:

Change in Social Communication Questionnaire (SCQ) score.

PK (Double-blind only):

- The plasma concentrations will be summarized by time window for CBD and its major metabolites following single and multiple doses of GWP42003-P. Where data allows, the area under the plasma concentration curve (AUC_{0-t}) from time zero to the last measurable time-point will be calculated.
- Plasma concentrations of concomitant AEDs before and after treatment with GWP42003-P, where available.

4. BLINDED DATA REVIEW MEETING

Prior to breaking the blind, it is anticipated that a Blinded Data Review Meeting (BDRM) will take place. The objectives of the meeting will include the identification and agreement on major protocol deviations and the need for a per protocol (PP) analysis set.

The meeting will have access to the following blinded summary tables and listings:

- Pre-randomization patient data
- Patient efficacy data
- Concomitant medication data
- Patient safety data
- Patient protocol deviation logs

This SAP documents the currently planned analyses for this trial that will be approved prior to breaking the blind for the trial. Changes to the analyses planned within any previously approved versions of the SAP will be summarized in Section 7 and integrated into the text of the SAP. The minutes of the BDRM will be documented separately.

5. STATISTICAL METHODS

5.1 General Considerations

In all tables, listings and figures for the double-blind phase, the trial medications will be referred to and labelled as per Table 1.

Table 1 Blinded Phase Trial Treatments

Endpoint	Actual Treatment	Treatment Label
Efficacy	Pooled Placebo	Placebo
Safety	25 mg/kg/day Placebo	Placebo 25 mg/kg
	50 mg/kg/day Placebo	Placebo 50 mg/kg
All	25 mg/kg/day GWP42003-P	25 mg/kg
All	50 mg/kg/day GWP42003-P	50 mg/kg

For safety tables where placebo is split by dosing volume, an additional Pooled Placebo column will be included.

For OLE tables, columns will be included for treatment received during the double-blind phase (GWP42003-P or placebo, i.e. not split by dose) and overall.

In all tables, listings and figures, the trial visits will be referred to and labelled as per Table 2.

Table 2 Trial Visits

Actual Visit	Visit Label
Visit 1: Screening	Day -35
Visit 2: Day -28, baseline visit	Day -28
Visit 3: Day 1, Randomization	Day 1
Visit 4: Day 15	Day 15
Visit 5: Day 29	Day 29
Visit 6: Day 43	Day 43
Visit 7: Day 57	Day 57
Visit 8: Day 71, Telephone	Day 71
Visit 9: Day 85	Day 85
Visit 10: Day 113	End of Treatment
Visit 11: Day 123	End of Taper
Visit 12: Day 151	Safety Follow-Up
Visit B1: Day 1, Enrollment	OLE Day 1
Visit B2: Day 15	OLE Day 15
Visit B3: Day 36	OLE Day 36
Visit B4: Day 92	OLE Day 92
Visit B5: Day 141, Re-stocking of supplies	OLE Day 141
Visit B6: Day 183	OLE Day 183
Visit B7: Day 232, Re-stocking of supplies	OLE Day 232
Visit B8: Day 274	OLE Day 274
Visit B9: Day 323, Re-stocking of supplies	OLE Day 323
Visit B10: Day 365	OLE End of Treatment
Visit B11: Day 375	OLE End of Taper
Visit B12: Day 389	OLE Post-taper Safety Telephone Call
Day 403	OLE Follow-Up

Unless stated otherwise, continuous variables will be summarized showing the number of non-missing values (n), mean, standard deviation, median, minimum and maximum and categorical variables will be summarized showing the number and percentage of patients falling in each category. For continuous summaries of seizure frequency, the lower and upper quartiles will also be presented.

Minimum and maximum values will be presented to the same decimal precision as the raw data. Mean and median will be presented to one more decimal place than the raw data, and standard deviation to 2 more decimal places than the raw data. Percentages will be presented to one decimal place.

Unless otherwise specified, tables for the blinded phases will be summarized by randomized treatment arm, and for the open-label extension phase will be summarized by double-blind randomized treatment arm and overall.

All analyses and summaries will be produced using SAS Version 9.3 or higher.

5.1.1 Missing Data

5.1.1.1 Handling of Missing Data for the Primary Efficacy Endpoint

If a patient withdraws during the treatment period, then the primary analysis variable will be calculated from all the available data, during the treatment period, including any data available after the patient withdraws.

Section 5.5.2.1 describes sensitivity analyses to account for missing data arising from unreported days in the interactive voice response system (IVRS), and missing data arising from patients withdrawing during the treatment period.

5.1.1.2 Handling of Missing Data for the Secondary Efficacy Endpoints

5.1.1.2.1 Quality of Life in Childhood Epilepsy (2–18 Years)

The calculations of subscale and overall scores for the QOLCE will treat responses of 'Not Applicable' as missing values.

For each subscale, if fewer than 50% of the items within the subscale are missing (including 'Not Applicable') then the subscale score will be calculated using the mean of the non-missing items. If 50% or more of the items within the subscale are missing then the subscale score will not be calculated and will be missing.

For the overall quality of life score, if less than 8 of the 16 subscale scores are missing then the overall quality of life score will be calculated using the mean of the non-missing subscale scores. If 8 or more of the subscale scores are missing then the overall quality of life score will not be calculated and will be missing.

5.1.1.2.2 Quality of Life in Epilepsy, Version 2 (19 Years and Above)

For missing questions within subscales, the following rule will be applied:

- For subscales containing 4 or more questions (not including the 'distress' item), apply the following:
 - If less than or equal to 50% of the questions within the subscale are missing then the converted score for the missing questions will be set to the average of the non-missing question converted scores.
 - If more than 50% of the questions within the subscale are missing then the subscale weighted score will be set to missing.
- For subscales containing less than 4 questions (not including the 'distress' item) the subscale weighted score will be set to missing.

For missing 'distress' items, the following rule will be applied:

- If the corresponding subscale weighted score is missing then no imputation is needed and the 'distress' item converted score will be missing.
- If the corresponding subscale weighted score is not missing then set to the average of the non-missing 'distress' item converted scores.

For missing subscale weighted scores or missing 'distress' item converted scores, the following rule will be applied when calculating the total score:

- If 3 or more of the 'distress' item converted scores are missing then the total score will be set to missing.
- If 3 or more of the subscale weighted scores are missing then the total score will be set to missing.

- If less than 3 'distress' item converted scores are missing and less than 3 subscale weighted scores are missing, then the total score will be calculated based on the available non-missing data, following the rules above.

Note: it is possible that a subscale weighted score is missing, but that the corresponding 'distress' item was answered and the converted score is not missing. Following the rules above, the total score would include the non-missing 'distress' item converted score in the calculation even though the corresponding subscale weighted score is missing and hence not included.

5.1.1.3 Adverse Events

Missing and/or incomplete dates/times for AEs will be imputed in a manner resulting in the earliest onset or the longest duration during the treatment period, taking into account that the start date/time should not be after the stop date/time. Stop dates/times will not be imputed if the AE is ongoing.

The imputation method will only be used to determine treatment emergence, and imputed dates/times will not be presented in AE outputs.

A worst-case approach will be followed in the event of missing severity or causality data. If the severity is missing, 'Severe' will be imputed. If causality data is missing, 'Yes' will be imputed for the question 'Plausible relationship to study medication'.

5.1.1.4 Concomitant Medication

Missing concomitant medication dates will be handled in a similar fashion as described for AEs in Section 5.1.1.3.

5.1.2 Day Numbering

Blinded Phase:

The first day of treatment (Day 1) will be taken from the Study Medication case report form (CRF) page at Visit 3. However, if this date is missing then the date of Visit 3 will be used.

Any days prior to Day 1 will be numbered relative to this day and calculated as:

Date - (Date of Day 1); to give Day -1, -2, -3 etc.

Any days post Day 1 will be calculated as:

1 + Date - (Date of Day 1)

Open-label Extension:

The first day of treatment in the OLE (OLE Day 1) will be day of entry into the OLE, which is expected to be the same day as the end of treatment visit from the blinded phase. OLE day will be calculated as above but relative to OLE Day 1.

5.1.3 Definitions

5.1.3.1 Baseline

For clinic visit based endpoints, baseline is defined as the last record or measure collected prior to the first dose of IMP.

For IVRS based endpoints, baseline will include all available data from the day of Visit 2 to Day 1 of the blinded phase.

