Each patient will take their first dose of IMP at Visit 3 (Day 1) and their final maintenance dose of IMP at Visit 10 (Day 113). If an unacceptable AE develops at any time during the titration period, dosing should initially be suspended or amended, at the investigator's discretion, until the event has resolved. During the maintenance period, patients should continue on a stable dosing regimen at the target Dose Level. If that dose becomes poorly tolerated or an AE occurs (e.g., somnolence, transaminase elevation **not meeting** withdrawal criteria specified in Section 10 and Section 12.8), the investigator may consider temporarily or permanently reducing the dosage for the remainder of the maintenance period following discussion with the GW medical monitor. It is recommended that patients with poor tolerability have their daily dose reduced by 10 mg/kg every seven days unless, in the investigator's opinion, smaller or

larger or more rapid dose reductions are clinically indicated. Where possible, the patient should be encouraged to return to the target Dose Level.

Patients entering the OLE will first complete a two-week blinded transition phase. OLE IMP will be titrated up to 25 mg/kg/day whilst blinded IMP is **simultaneously** tapered down to zero. All patients will complete the transition and enter the OLE taking 25 mg/kg/day GWP42003-P.

Following completion of the blinded transition patients may complete a three-week titration up to a target dose of 50 mg/kg/day. Beginning at 25 mg/kg/day the dose will increase in increments of 2.5 mg/kg/day every two days.

Table 8.1.2-2	Blinded Transition					
Day Blinded	Patients randomized to 25 mg/kg/day group				Patients randomized to placebo group	
Transition/OLE	Blinded	Open-label	Blinded	Open-label	Placebo	Open-label
1	25	0	50	0	0	0
2	22.5	0	45	0	0	0
3	20	5	40	5	0	5
4	17.5	5	35	5	0	5
5	15	10	30	10	0	10
6	12.5	10	25	10	0	10
7	10	15	20	15	0	15
8	7.5	15	15	15	0	15
9	5	20	10	20	0	20
10	2.5	20	5	20	0	20
11	0	25	0	25	0	25
12	0	25	0	25	0	25
13	0	25	0	25	0	25
14	0	25	0	25	0	25

Table 8.1.2-2 is an example of the OLE transition (Visit B1 to Visit B2) for patients transitioning from each group of the randomized phase.

Following completion of the blinded transition patients may complete a three-week titration up to a target dose of 50 mg/kg/day. Beginning at 25 mg/kg/day the dose will increase in increments of 2.5 mg/kg/day every two days (Table 8.1.2-3).

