5.1.3.4 Treatment Period

The treatment period of the double-blind phase is defined as Day 1 to Day 113.

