5.1.3.5 Titration Period

The titration period of the double-blind phase is defined as Day 1 to Day 28.

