5.1.3.6 Maintenance Period

The maintenance period of the double-blind phase is defined as Day 29 to Day 113.

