5.5.2.1.1 Sensitivity Analysis of Missing Data

Missing data in this trial could potentially arise from the mechanism of MNAR. Hence, a sensitivity analysis is required to assess the potential impact that missing data under the mechanism of MNAR may have on the estimated results for the primary endpoint.

To facilitate multiple imputation techniques for missing data due to patients who withdraw from the treatment period, it is necessary to divide the treatment period into smaller periods for which missing seizure data can be imputed. Hence, sensitivity analysis of the primary endpoint will be carried out based on periods corresponding to each 14 days of the

treatment period, by multiple imputations on the average daily TSC-associated seizure frequency. The final period will consist of 15 days to include Day 113, where applicable. Following imputation, the imputed periods will be recombined for each patient in order to repeat the primary analysis.

For each 14 calendar days of the treatment period (15 days for the final period), the average daily TSC-associated seizure frequency will be calculated as:

$$(\text{Number of TSC-associated seizures in the period} \div \text{Number of reported days in IVRS in the period})$$

For patients with <6 days in a period, the frequency will be set to missing and will be imputed as part of this analysis.

For intermittent missing data, in which subjects have missing values for intermediate periods but have available data at subsequent periods, imputation will be based on the MCMC methodology. Assumptions underlying this partial imputation step are that patients will follow a similar outcome trajectory as patients in their respective treatment arm that have complete data. Intermittent missing values will be imputed using the MCMC method in PROC MI with an IMPUTE=MONOTONE statement for 200 times for each treatment arm separately. To avoid negative results, a minimum of 0 will be specified in the PROC MI statement. As a result, missing intermediate visits will be imputed and the resulting 200 partially imputed datasets will have a monotone missing pattern.

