5.6 Safety Evaluation

5.6.1 Exposure to IMP

Blinded Phase:

Patients are required to take IMP twice daily (morning and evening). The first dose will be taken in the clinic on Day 1. The date of final dose in the treatment phase will be recorded on the CRF. The date of final dose, for patients who enter the taper period, will be recorded on the CRF at the end of taper visit.

The total number of dosing days in the treatment phase will be calculated as:

$$(\text{Date of last dose in the treatment phase} - \text{Date of Day 1}) + 1$$

The date of last dose in the treatment phase will be obtained from the CRF at the end of treatment visit.

Any missed doses during treatment should be recorded on the 'IMP Missed Doses Log' CRF page. The number of days with any missed doses and the number of days where trial medication was not taken in the AM nor PM will be summarized based on data in the treatment phase (Day 1 to end of treatment visit).

In addition, the number of days in which trial medication was taken at least once (AM or PM) will be summarized and calculated as:

$$\text{Total number of dosing days} - \text{the number of days where trial medication was not taken in the AM nor PM}$$

The number of days in which trial medication was taken both AM and PM will be summarized and calculated as:

$$\text{Total number of dosing days} - \text{the number of days with any missed doses}$$

The above summaries will be presented for all patients and repeated for patients who completed the treatment phase.

In addition, the expected daily volume of IMP to be administered during the treatment phase, once a patient has titrated to target dose, will be summarized by treatment.

The expected daily volume of IMP will be calculated as:

$$2 \times [\text{Weight (kg) at Day 1} \div 8 \text{ and rounded to the nearest 0.1}]$$

for patients randomized to the 25 mg/kg/day dose level and:

$$2 \times [\text{Weight (kg) at Day 1} \div 4 \text{ and rounded to the nearest 0.1}]$$

for patients randomized to the 50 mg/kg/day dose level.

Finally, IMP compliance will be summarized by treatment and calculated as:

$$100 \times (\text{Number of days IMP taken at least once} + \text{number of days IMP taken both AM and PM}) \div (2 \times \text{day of completion or withdrawal during the treatment period})$$

Open-label Extension:

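### As worded, the SAP counts Day 1 in both the IVRS baseline and the treatment period; the baseline should end on Day -1

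*SAP*

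**What the plan says.** SAP 5.1.3.1 sets two baselines. For clinic-visit endpoints it takes the last value before the first dose. For IVRS endpoints, "baseline will include all available data from the day of Visit 2 to Day 1 of the blinded phase".

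SAP 5.1.3.4: "The treatment period of the double-blind phase is defined as Day 1 to Day 113".

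Day 1 is the first dosing day. SAP 5.1.2: "The first day of treatment (Day 1) will be taken from the Study Medication case report form (CRF) page at Visit 3". SAP 5.6.1: "The first dose will be taken in the clinic on Day 1". Protocol 8.1.2 agrees, placing the first dose at Visit 3.

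SAP 5.5.2 refers to both period definitions for the primary endpoint. The baseline and treatment totals are the two responses in one negative binomial model, and the log of the reported days is the offset.

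The protocol's Definition of Terms gives baseline a length of 28 days, with a 3-day allowance, ending at randomization. Protocol 9.1.1.3 places Visit 3 28 days (+3) after Visit 2. Protocol 13.6.1 starts the evaluable period on Day 1.

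**The concern.** A baseline should describe the patient before treatment, and the two counts being compared should come from different days. Here one calendar day, which includes the first dose, sits in both. Its seizures are added to both totals and its reported day to both offsets.

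The same baseline definition feeds the 50% responder analysis (first key secondary), total seizures (third key secondary), seizure-free days, the baseline covariate in the multiple imputation and the baseline tertile subgroups. In the time-to-baseline-frequency analysis (SAP 5.5.4.10), Day 1 seizures help to set the threshold and also count towards reaching it.

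The rule also leaves room for two programmers to derive different baseline counts, one from the SAP wording and one from the protocol's 28 days.

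**Working it through.** **1. Does 'to' include the end day?** The neighbouring definitions show that it does. Titration: "The titration period of the double-blind phase is defined as Day 1 to Day 28". Maintenance: "The maintenance period of the double-blind phase is defined as Day 29 to Day 113". These join without gap or overlap only if both end days are included. SAP 5.5.2.1.1 confirms that Day 113 is in: "The final period will consist of 15 days to include Day 113", and 7 × 14 + 15 = 113. No section removes Day 1 from the IVRS baseline or splits it at the time of dosing.

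**2. The protocol's baseline length.** The SAP day numbering has no Day 0, and Visit 3 (Day 1) is 28 days after Visit 2.

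- Day of Visit 2 to Day -1: 28 days, or 31 with the +3 window. This reproduces the protocol's 28 (+3).
- Day of Visit 2 to Day 1: 29 days, or 32 with the window.

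The shared day is 1/29 = 3.4% to 1/32 = 3.1% of baseline days, and 1/113 = 0.9% of treatment days.

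**3. Effect on the tested ratio.** Inputs from SAP 3.2: reductions of 50% on active and 15% on placebo, used here as rate ratios of 0.50 and 0.85. Let B be the number of pre-dose baseline days. Let d be the Day 1 seizure rate divided by the pre-dose daily rate. The documents give no d, so these values are assumptions. Including Day 1 multiplies an arm's baseline rate by (B + d)/(B + 1), so the active-to-placebo ratio becomes

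(0.50/0.85) × (B + d_placebo)/(B + d_active).

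| Assumed Day 1 effect | d active | d placebo | Ratio, B = 28 | Reduction, B = 28 | Ratio, B = 31 |
|---|---|---|---|---|---|
| None | 1 | 1 | 0.5882 | 41.18% | 0.5882 |
| Half of the planned effect | 0.75 | 0.925 | 0.5918 | 40.82% | 0.5915 |
| All of the planned effect | 0.50 | 0.85 | 0.5955 | 40.45% | 0.5948 |
| Extreme: no active seizures on Day 1 | 0 | 0.85 | 0.6061 | 39.39% | 0.6044 |

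Half to full effect costs 0.36 to 0.73 percentage points of apparent reduction. The direction depends on the assumption. If Day 1 seizures rose by 25% on active and not on placebo, the ratio would be 0.5882 × 29/29.25 = 0.5832, away from the null.

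**4. Correlation from the shared day.** With Poisson counts at equal daily rates it is 1/√(29 × 113) = 0.017.

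**5. Responder status.** Take a patient at the eligibility minimum of 8 seizures in 28 days (Protocol 6.1.11), with complete reporting. The 50% limit over 113 days is half the 28-day baseline frequency × 113/28.

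| Baseline rule | Baseline per 28 days | Limit over 113 days |
|---|---|---|
| Day 1 excluded | 8.0 | 16.1 |
| Day 1 included, 0 seizures that day | 8 × 28/29 = 7.7 | 15.6 |
| Day 1 included, 3 seizures that day | 11 × 28/29 = 10.6 | 21.4 |

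The limit can become stricter or easier, depending on one day's count.

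**6. Sample size.** The calculation uses the two mean reductions, a standard deviation of 60% and 70 patients per arm. Baseline length is not an input, so the stated 90% power does not change.

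**The case against.** The strongest reply is that this is loose wording and the intent is clear elsewhere. The SAP is based on a protocol whose baseline is 28 (+3) days, ends at randomization and is called pre-randomization in Protocol 4.1.2. The SAP's own rescue-medication rule (5.5.4.3) describes its periods as lying between visits. On that view 'to Day 1' means up to Day 1. That may well be what was intended, but it is not how 'to' works in the adjoining definitions, and SAP 5.8 on changes to the planned analysis does not address it. An argument that the Day 1 call reports pre-dose hours would not help either: it would place the record in baseline only, not in both periods.

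Three further points on the other side stand:

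- Day 1 is only partly a treated day. The first dose follows the Visit 3 assessments and is at the lowest titration step, so a large fall in seizures that day has no support in the documents.
- The model already has a patient random effect, and an added correlation of 0.017 is negligible.
- The sensitivity analyses on the maintenance period (Day 29 to Day 113) share no day with baseline. They remove the double use, although Day 1 stays in their baseline.

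A reader might infer that the overlap always biases towards the null and is therefore safely conservative. The documents do not support that. It holds only if Day 1 seizures fall more on active than on placebo, and no Day 1 effect is stated.

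**Conclusion.** The overlap is real as the SAP is worded. Day 1 belongs to both periods, and the IVRS baseline is one day longer than the protocol's.

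Its effect on the primary comparison is small. Under the planned reductions and an assumed half to full effect on Day 1, the ratio moves from 0.588 to between about 0.592 and 0.596. With no Day 1 effect, or an equal one in both arms, the ratio is not biased. Single patients near the 50% limit can change responder status in either direction.

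A reader might go further and infer that the primary result, the power or the error control is compromised. Nothing here shows that: the shift is under one percentage point in the half-to-full scenarios, and the sample size and testing hierarchy are untouched. Nor do the documents show how the derivation was actually programmed. The correction is still worth making, because this is a stated rule that feeds the primary endpoint and two of the three key secondary endpoints, and it disagrees with the protocol.

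**What to change.** In SAP 5.1.3.1, define the IVRS baseline as running from the day of Visit 2 to the day before Day 1 (Day -1). Leave the treatment period in 5.1.3.4 as Day 1 to Day 113. The same derived baseline count and reported-day offset should then feed every analysis that uses the IVRS baseline.

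The cost is one line of text. No data are lost: Day 1 stays in the treatment period, and baseline keeps 28 to 31 days, as the protocol intends. If the derivation has already been programmed, check it on a patient with Visit 3 exactly 28 days after Visit 2 and complete reporting. It should give 28 baseline days and 113 treatment days, with none in common.
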